# Visit 1: Study Entry (Day -14)

On Visit 1 (Day -14), subjects (or legally authorized parent or guardian) will sign a written informed consent, or assent when applicable. Baseline procedures will include evaluation of eligibility criteria and recording or obtaining demographics, medical history, physical examination, height, weight, body mass index, vital signs, standard clinical laboratory tests (hematology, clinical chemistry, urinalysis), blood lipids, urine sample for urinary leukotriene evaluation, plasma fatty acid sample, pregnancy test for childbearing females and concomitant medications. Collected results on Day -14 will be used to screen patients for eligibility and characterize the study population. Study staff will also review the medical records and obtain up to four body weight measurements recorded at 3 month intervals over the previous 12 months. Historical average daily PERT use with meals and snacks and with enteral nutrition will be recorded. Study staff will provide detailed instructions for subjects to maintain a gastrointestinal symptom diary for 7 consecutive days.

During the observation period (Day -14 to Day -8), subjects will maintain their usual care plan. The brand, volume, and administration rate of the enteral formula used in the enteral feeding will be recorded, along with the usual dose of PERT use associated with the enteral feeding. Crushing of PERT products and adding to the enteral feeding bag is prohibited. Subjects will make entries into a 7-day gastrointestinal symptom

Title: Absorption and Safety with Sustained Use of Relizorb™ Evaluation (Assure) Study in Patients With Cystic Fibrosis Receiving Enteral Feeding

diary each day. PERT use with meals and snacks and with enteral tube feeding will be recorded each day by the subject.

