6.3 Derived Variables

The following derived variables have been initially identified as important for the analysis of the safety and efficacy endpoints. It is expected that additional variables will be required. The SAP will not be amended for additional variables that are not related to the primary target or key secondary target variables. Any additional derived or computed variables will be identified and documented in the SAS programs that create the analysis files. If the SAP is not amended, further derivations related to primary and secondary target variables will be described in the CSR.

- Baseline = the last non-missing measurement before the date of RELiZORB administration for safety assessments. For efficacy assessments, baseline will be the assessment collected at Visit 2 (Day 0). However, if the result from Visit 2 is missing and the result from Visit 1 is available, the result from Visit 1 will be used.
- Study Entry = Day -14, which occurs during Study Visit 1.
- Study day = Assessment Date Date of first RELiZORB administration (+ 1 if assessment date is on or after date of first RELiZORB administration).
- Change from Baseline = Value at Post Baseline Value at Baseline.
- % Change from Baseline = 100 * Change from Baseline / Value at Baseline.
- "End of Study" is the point at which the last contact with the subject during the protocolspecified schedule is made.
- "Screen Failure" is a subject who has not met eligibility criteria.

The years of enteral tube feeding will be calculated from the first date of gastrostomy tube placement in the medical history to the Visit 1 date. For partial dates, if the day is missing, the first will be used. If the month and day are missing, January 1 will be used. The years will be calculated as (Visit 1 date – date of gastrostomy tube placement)/365.25.

The following subgroups will be used for subgroup analyses of selected endpoints:

- Age Categories: <=12 years, 13-18 years, and >=19 years.
- CFRD Categories: CRFD and non-CFRD. CFRD will include all subjects who
 reported "cystic fibrosis related diabetes", "CFRD", "type 1 diabetes mellitus",
 "diabetes mellitus related to cystic fibrosis" in their medical history.

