6.3.1 Weight and BMI Derived Variables

Up to 4 weight, height, and body mass index (BMI), (and BMI percentile for subjects of age ≤18 years) recordings will be obtained from the medical record at approximately 3 month intervals over the previous 12 months prior to Visit 1 on Day -14. Weight and BMI will be collected at Visit 1 (study entry; Day -14) and at study visits on Day 0 (Visit 2), Day 30 (Visit 3), Day 60 (Visit 4), and Day 90 (Visit 5).

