6.3.1.1 Weight Gain Velocity

Weight gain velocity (WGV) is defined as the rate of change in body weight per initial body weight per time period. The quantity will be expressed in units of g/kg/90 days.

The formula to calculate WGV between two dates Date1 and Date2 is:

90 x [weight (g) at Date2 – weight (g) at Date1] / [weight (kg) at Date1] / (Date2 – Date1 + 1)

The factor of 90 converts the rate from per day to per 90 days.

The WGV can be considered the slope as the change in weight (Δ w) divided by the change in days plus 1 (Δ t). This quantity is multiplied by 90 and then divided by the subject weight at interval start (kg) to express the results as 90-day changes for each kilogram of weight. For example, if a patient is 62.0 kg on January 1, 2016 and 63.5 kg on April 1, 2016, the slope is 1.5 kg/92 days = 1.5 kg/92 days = 1500 g/92 days = 16.3 grams per day. Equivalently, 90 days x 16.3 g/day equals 1467.4 g / 90 days. Expressed per kg body weight, the WGV equals 23.7 g/kg/90 days. Equivalently, as above, 90*(63500-62000)/62.0/92 = 23.7

WGV will be calculated from the date of Visit 2 to the date of Visit 5, or the last visit at which a weight is available.

The historical weight recordings will be used to calculate historical WGV. Any weights recorded more than 12 months before Study Entry and weights recorded before the date of tube placement indicated in medical history will be excluded. The selection of the appropriate medical indications and date imputations for this are described in Section 6.3 for the calculation of duration of enteral feeding. The historical WGV will be determined by first calculating the change in weight between each consecutive historical weight recorded before Study Entry and thus providing up to 3 values for change in weight. WGV will then be calculated from these weight changes as described above. The average of these values will be determined and identified as the average historical WGV.

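### Historical weight gain velocity averages interval slopes without regard to interval length, so unevenly spaced chart weights can distort it, and the partial tube-date rule can keep pre-tube weights that the SAP means to exclude

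*SAP*

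**What the plan says.** SAP 6.3.1.1 defines WGV between two dates as the weight change in grams, divided by the starting weight in kilograms and by elapsed days plus one, times 90. For the historical value it takes the change between "each consecutive historical weight recorded before Study Entry and thus providing up to 3 values for change in weight". Each change becomes a WGV, and then "The average of these values will be determined and identified as the average historical WGV". No weighting by interval length, minimum gap or spacing tolerance is stated.

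The weights come from the medical record. SAP 6.3.1 asks for them "at approximately 3 month intervals over the previous 12 months" before Visit 1. The Protocol, under Visit 1, tells staff to "obtain up to four body weight measurements recorded at 3 month intervals over the previous 12 months". The ±4-day window in both documents applies to study visits, not to chart weights.

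SAP 6.3.1.1 also excludes weights that predate tube placement. It borrows the date imputation of SAP 6.3, which was written for duration of enteral feeding. There a missing day becomes the first of the month, and "If the month and day are missing, January 1 will be used".

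SAP 8.3.1 tests the change from historical to study WGV by age subgroup, with a one-sample t-test or a signed rank test. SAP 2.2.2 lists this endpoint as exploratory.

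**The concern.** A velocity over a short interval divides ordinary weight fluctuation by few days. It therefore carries a large error, yet counts as much as one over a long interval. Retrospective chart weights need not be evenly spaced, and nothing in the derivation guards against a short gap. The historical value is the comparator in the WGV test, which is run within age subgroups of a study planned for about 30 evaluable subjects, so added noise costs precision there.

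The tube-date rule is a separate, logical problem. The earliest consistent date is a workable convention for a duration. For an exclusion rule it can err in only one direction: it can keep a weight taken before the tube, but it can never wrongly drop one taken after it. It therefore works against the exclusion that the SAP itself sets.

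**Working it through.** **The plan's own figure.** From 1 January to 1 April 2016 is 91 days, plus one is 92: 90 × 1500 / 62.0 / 92 = 23.67. This agrees with "Equivalently, as above, 90*(63500-62000)/62.0/92 = 23.7".

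**Precision of the historical WGV.** Assumptions, none of them in the documents: body weight near 30 kg; an independent error with SD 0.5 kg on each weight; four weights over 270 days; no true variation between subjects in the change of growth rate. The scale factor is 90 × 1000 / 30 × 0.5 = 1500.

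- SAP mean: SD = 1500 × √(Σc²), where c are the coefficients on the four weights when each interval contributes 1/[3(d + 1)].
- Least-squares slope on date: SD = 1500 / √Sxx.
- Study WGV, Day 0 to Day 90: SD = 1500 × √2 / 91 = 23.3, variance 543.4.

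For 30/90/150 days, c = −0.01075, 0.00709, 0.00146, 0.00221, so Σc² = 0.0001729 and SD = 1500 × 0.01315 = 19.7. The weights fall on days 0, 30, 120 and 270 (mean 105), so Sxx = 11025 + 5625 + 225 + 27225 = 44100 and SD = 1500 / 210 = 7.1. The paired-difference variance ratio is (543.4 + 389.0) / (543.4 + 51.0) = 1.57.

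| Spacing (days) | SAP mean, SD | Least squares, SD | Paired-difference variance ratio |
|---|---|---|---|
| 90/90/90 | 7.8 | 7.5 | 1.01 |
| 75/90/105 | 8.2 | 7.4 | 1.02 |
| 60/90/120 | 9.7 | 7.4 | 1.07 |
| 45/90/135 | 12.8 | 7.3 | 1.19 |
| 30/90/150 | 19.7 | 7.1 | 1.57 |

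SDs are in g/kg/90 days. Total change over total elapsed days gives SD 1500 × √2 / 271 = 7.8 at every spacing in the table.

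**One fluctuation.** Take steady growth of 25 g/kg/90 days from 30 kg, and add 0.5 kg to the third weight only. At 91/91/91 days the SAP mean barely moves, from 24.1 to 24.2. At 122/30/121 days it moves from 24.0 to 35.6, while the least-squares slope moves from 25.0 to 25.6. The end-to-end value stays at 24.9, since it does not use that weight.

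**Tube date.** An invented case: Study Entry on 1 June 2016; true placement on 15 November 2015; weights on 30 August and 10 November 2015 and on 10 February and 10 May 2016.

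| Tube date as recorded | Date applied under SAP 6.3 | Weights kept | Of these, pre-tube |
|---|---|---|---|
| Complete | 15 Nov 2015 | 2 | 0 |
| Day missing | 1 Nov 2015 | 3 | 1 |
| Month and day missing | 1 Jan 2015 | 4 | 2 |

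In the last row two of the three slopes start before the tube. Under the latest consistent date (30 November or 31 December 2015) both partial records keep only the two eligible weights.

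**The case against.** The plan intends roughly quarterly weights. At that spacing the plain mean is as precise as the end-to-end slope, and averaging velocities over about 90 days mirrors the 90-day study velocity. This stands. A reader might infer that a short interval routinely dominates the historical WGV, but the documents do not support that: they give no actual spacing, and nothing in them points to 30-day or 45-day gaps. Most of the error in the paired difference also comes from the two-point study velocity. If true change varied between subjects with an assumed SD of 20 to 30 g/kg/90 days, the factor of 1.57 would fall to between 1.34 and 1.23.

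The tube-date problem needs both a partial date and a placement inside the 12-month look-back. Protocol 4.9.4 asks for at least a year of history with emphasis on surgery, so recent placements should often be well dated. That makes the problem less likely but does not remove it: the SAP itself provides for partial dates, and Protocol 4.4.1 sets no minimum time since placement.

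A reader might also infer that pre-tube weights bias the comparison towards RELiZORB. Protocol 2.3 describes tube feeding as support for nutritionally challenged patients, so slower growth before the tube is plausible. No figure documents it, however, and an interval that straddles placement includes growth after it.

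Nor is historical WGV the only yardstick for weight. SAP 8.3.2 compares weight and BMI percentiles with their historical average, and Protocol 7.8 analyses absolute weight change from Day 0.

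**Conclusion.** The point holds as a minor, conditional defect in a derived variable. The equal weighting and the lack of a minimum gap are plain in the text. The loss is trivial near the planned spacing and material only when one gap is far below 3 months: the paired-difference variance rises by 1% at 90/90/90 days, 7% at 60/90/120 and 57% at 30/90/150. These sizes rest on the assumed 0.5 kg error, the 30 kg weight and no between-subject variation.

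The tube-date flaw follows from the rule itself and needs no assumed error size. How many subjects it touches is not given, and its direction is likely but undocumented. The primary analysis and the sample size are unaffected.

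**What to change.** Define historical WGV as total weight change over total elapsed days across all eligible historical weights, or as their least-squares slope on date, scaled by the first eligible weight. The end-to-end form has the same two-point structure as the study WGV. At equal spacing almost nothing changes: in the steady-growth example at 91/91/91 days the value goes from 24.1 to 24.9, mainly because the first weight replaces each interval's own starting weight as the divisor.

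For the weight exclusion only, set a partial tube date to the latest date consistent with the record, not after Visit 1. Leave the rule for duration of feeding as it is. Report the comparison under the current rule as a sensitivity analysis.

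The cost is a few lines of SAP text and one change to a derived variable, plus some data. A missing day can drop weights from the placement month. A year-only date in the entry year resolves to Visit 1, which removes every historical weight and takes that subject out of this exploratory comparison. In small age subgroups that matters, so the number of subjects affected should be reported alongside the sensitivity analysis.

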6.3.1.2 Weight and BMI Z-scores and Percentiles Derived Variables

Weight and BMI values from baseline (Visit 2 or Visit 1 if Visit 2 is missing) and Visit 3 to Visit 5 will be normalized to Z-scores based on age- and sex-specific data from the Centers for Disease Control and Prevention (CDC). A SAS program and dataset obtained from the CDC website will be used to calculate the values for healthy subjects aged 2-20 years, with age expressed in months with decimal. The CDC data is provided in half month intervals for age.

6.4 Lower and Upper Limit of Quantification

For analysis, all laboratory values will be presented in standard (SI) units.

In general, for quantitative laboratory values reported as "<" or "\le " the lower limit of

CONFIDENTIAL

quantitation (LLOQ) or limit of detection (LOD), one-half of the reported value (i.e., LLOQ/LOD) will be used for analysis.

For quantitative laboratory values reported as ">" or "\geq" the upper limit of quantitation (ULOQ), the reported value (i.e., ULOQ) will be used for analysis.

7. STUDY SUBJECTS AND DEMOGRAPHICS

7.1 Disposition of Subjects and Withdrawals

All subjects who provide informed consent will be accounted for in this study. The total number of subjects screened, screen failures and enrolled will be summarized.

In addition, tabulations of the number of subjects who completed the study, and discontinued early from the study (along with the reasons for withdrawal) will be provided. The subject disposition tabulation will also include the number of subjects in each of the analysis populations.

7.2 Protocol Violations and Deviations

Protocol violations and deviations will be recorded in the CRF and reviewed prior to database lock.

Violations and deviations will be categorized into the following categories:

- Inclusion/exclusion criteria
- Informed consent form (ICF)
- Missed study procedure or visit
- Out of window procedure or visit
- Investigational product noncompliance
- Other

Other protocol deviation categories may be identified during the study. Protocol deviations and violations will be recorded and referenced to determine the subjects to be excluded from the per protocol population. The final decision regarding inclusion and exclusion of subjects from the analysis populations will be based on a listing of protocol deviations. This will be determined during a data review meeting before database lock, with input from Clinical and Biostatistics team members and approval from the Sponsor.

Protocol deviations will be summarized by type (deviation or violation), major or minor, and by category for all enrolled subjects.

7.3 Demographics and Other Baseline Characteristics

Baseline demographics and characteristics (age, age category, gender, race, ethnicity, height, weight, and BMI) duration (years) of enteral tube feeding (EF) prior to study entry, females of child bearing potential, physical exam (normal, abnormal), and CFRD subgroup will be presented. Subjects reporting more than 1 race will be counted in a "Multiple" category.

The years of enteral tube feeding will be calculated from the first date of gastrostomy tube placement in the medical history to the Visit 1 date. For partial dates, if the day is missing, the first will be used. If the month and day are missing, January 1 will be used. The years will be calculated as (Visit 1 date – date of gastrostomy tube placement)/365.25.

Subject demographics and baseline characteristics will also be presented in a subject listing.

Whether a subject met all inclusion/exclusion criteria will be included in a listing. Any criteria not met will be included.

7.4 Medical History

All medical history information will be presented in a subject listing.

8. EFFICACY ANALYSIS

The primary analysis population for all efficacy analyses will be the ITT population. The analysis of erythrocyte membrane composition (%) of DHA+EPA will be repeated using the PP population.

8.1 Primary Efficacy Endpoint

Fatty acid erythrocyte tissue composition of the total of DHA plus EPA is the primary efficacy endpoint and is measured at visits 1 through 5 on days -14, 0, 30, 60, and 90, respectively. The primary efficacy endpoint (actual values) will be analyzed by a mixed model repeated measures (MMRM) model to test for LS Mean differences relative to baseline (as defined in Section 6.3) among the post-baseline visits. For this analysis, study visit 2 (day 0), 3 (day 30), 4 (day 60), 5 (day 90) is a categorical effect and subject is a random effect. The primary study population compares baseline to Day 90 in the ITT population. For subjects who lack visit 2, the value at visit 1 will be used.

An unstructured within-subject covariance matrix will be used. If the model does not converge, auto-correlated, and compound symmetry will be explored and the model resulting in the lowest Akaike information criterion value will be presented. LS Means, standard errors (SE), and 95% confidence intervals will be reported by visit. Contrasts in LS Means at each visit against baseline will also be reported with SE and 95% confidence intervals with p-values for differences from zero. A sensitivity analysis of the primary efficacy endpoint will be conducted in the PP population.

Summary statistics for actual values at each visit and changes from baseline will be presented.

The primary endpoint analysis will be repeated by age subgroups and by CFRD subgroups separately.

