Serial measurements (Days 0, 30, 60, and 90) of plasma concentrations and erythrocyte levels of LCPUFAs such as DHA and EPA, plasma concentrations of other long chain fatty acids, plasma concentrations of fat soluble vitamins, serum protein and concentrations, urinary leukotriene concentrations, and body weight and BMI will be obtained and compared with each other as well as with values obtained at study entry (Day -14).

Safety and tolerability will be assessed using a gastrointestinal symptom diary, as well as recording adverse events (AEs), and unanticipated adverse device effects (UADEs).

Title: Absorption and Safety with Sustained Use of Relizorb™ Evaluation (Assure) Study in Patients With Cystic Fibrosis Receiving Enteral Feeding

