## 7.8 Efficacy Analysis

The measurement of the absorption of fats is an important efficacy endpoint, using absorption of fatty acids as surrogate biomarkers for fat absorption. LCPUFA plasma concentrations such as DHA and EPA will be an outcome variable, along with tissue accretion of LCPUFAs, measured as relative levels in erythrocyte membrane, and the profile of fatty acids in plasma. The fatty acid profile will also be used to calculate the ratio of omega-6 to omega-3 fatty acids, another outcome variable. Fat-soluble vitamin (A, D, and E) concentration is an additional efficacy endpoint and will be used as a laboratory outcome variable. Serum protein (total protein, prealbumin, albumin, and transferrin) concentrations and urinary leukotriene concentrations are additional endpoints and also represent laboratory outcome variables.

For all laboratory outcome variables, mean values from samples obtained on Day -14 and Day 0 will be compared using a two-sided test for comparison. The mean value from samples obtained on Day 0 will be used as the baseline for comparison with mean values from samples obtained on Days 30, 60, and 90 using ANOVA.

Body weight, height, and BMI are endpoints and clinical outcome variables. Absolute change in body weight from Day 0 through Days 30, 60, and 90 will be analyzed using ANOVA. To evaluate the effect of Relizorb use on weight and BMI, up to 4 weight and BMI recordings obtained from the medical record at 3 month intervals over the previous 12 months. The historical weight recordings will be used to calculate historical weight gain velocity, expressed as grams of body weight per kilogram of body weight per day. The study weight gain velocity will be similarly calculated by using the body weight values obtained on Days 0, 30, 60, and 90. The historical weight gain velocity will be compared to the study weight gain velocity using a two-sided test for comparison. In addition, the historical weight and BMI recordings, along with the weight and BMI values recorded on Day 0, will be used to calculate a standard score for weight and BMI values recorded on Days 30, 60, and 90.

Title: Absorption and Safety with Sustained Use of Relizorb™ Evaluation (Assure) Study in Patients With Cystic Fibrosis Receiving Enteral Feeding

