#### Ingredients of Peptamen® 1.5 (Unflavored):

Water, Maltodextrin, Enzymatically Hydrolyzed Whey Protein (from Milk), Medium Chain Triglycerides (from Coconut and/or Palm Kernel Oil), and less than 2% of Cornstarch, Soybean Oil, Soy Lecithin, Magnesium Chloride, Sodium Ascorbate, Sodium Phosphate, Calcium Phosphate, Guar Gum, Calcium Citrate, Choline Chloride, Potassium Chloride, Salt, Sodium Citrate, Taurine, L-Carnitine, Magnesium Oxide, Alpha-Tocopheryl Acetate, Zinc Sulfate, Ferrous Sulfate, Niacinamide, Calcium Pantothenate, Vitamin A Palmitate, Potassium Citrate, Manganese Sulfate, Pyridoxine Hydrochloride, Vitamin D3, Copper Sulfate, Thiamine Mononitrate, Riboflavin, Beta Carotene, Folic Acid, Biotin, Citric Acid, Potassium Iodide, Chromium Chloride, Sodium Selenate, Sodium Molybdate, Phytonadione, Vitamin B12.

\* MCT provides 10 g/250 mL

\*\* Includes 37% of vitamin A activity from beta-carotene

Title: Absorption and Safety with Sustained Use of Relizorb™ Evaluation (Assure) Study in Patients With Cystic Fibrosis Receiving Enteral Feeding

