3.2 Sample Size

The proposed study with 30 complete and evaluable subjects would have 80% power to detect a minimum effect size of 0.53. Based on literature reviews using 1.5% as the maximum standard deviation expected when measuring DHA levels in plasma, the study should be able to detect an absolute increase of at least 0.8% from the baseline DHA value after 90 days of RELiZORB use (i.e., a change from 3.0% at baseline to 3.8% after 90 administration days or a 27% relative increase). This sample size will be adequate to detect the desired 30% relative increase in DHA levels.

The primary efficacy endpoint for this study is the sum of DHA+EPA. The sample size was based on a literature review of DHA assuming an effect size of 0.53. Assuming the same effect size for measuring erythrocyte tissue composition of the total of DHA plus EPA is consistent with that of DHA, the current sample size will provide 80% power.

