6. GENERAL ISSUES FOR STATISTICAL ANALYSIS

6.1 General Statistical Methodology

The primary population for safety is the safety population. For the efficacy analysis, the primary endpoint will be conducted on both the per protocol (PP) and ITT populations. All secondary efficacy analyses will be conducted on the ITT population unless otherwise specified.

Continuous variables will be summarized using descriptive statistics, including number of nonmissing values, mean, standard deviation, median, minimum, and maximum. Qualitative variables will be summarized using the number and proportion of each possible value.

The minimum and maximum will be reported with the same degree of precision (i.e., the same number of decimal places with a maximum of 1 decimal place) as the raw data. Measures of location (mean and median) will be reported to 1 degree of precision (with a maximum of 2 decimal places) more than the raw data and the measure of spread (standard deviation) will be reported to 2 degrees of precision (with a maximum of 3 decimal places) more than the raw data. All efficacy endpoints in section 8.1 will use a maximum of two decimal places.

Categorical (qualitative) variable summaries will include the frequency and percentage of subjects who are in the particular category. The denominator for the percentage calculation will be based upon the total number of subjects in the relevant study population unless otherwise specified.

Assessments done on unscheduled visits will not be summarized but will be listed. If any assessments are repeated on the same day and/or time point, the last non-missing assessment will be summarized and/or analyzed.

Statistical tests will be conducted at the 0.05 significance level using 2-tailed tests, and nominal p-values will be reported. SAS software (SAS, Inc., Cary, NC) will be utilized for statistical analysis (version 9.3).

Subject level information presented in a listing will include subject identification number as well gender, age (examples: F/23, M/37). All listings will be sorted by subject identification numbers.

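### The SAP specifies no Day -14 contrast although the protocol plans one, so a run-in shift in the Day 0 baseline would have no paired estimate or interval

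*SAP*

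**What the plan says.** Subjects spend Day -14 to Day -8 on their usual regimen. They then use Peptamen 1.5 for at least 5 days between Day -7 and Day -1 (Protocol 4.3). Protocol 11.1 gives 14 g fat per 250 mL, and its footnote says "MCT provides 10 g/250 mL". The ingredient list has no fish oil.

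Day 0 is the baseline for the treatment comparisons in both documents. The protocol also uses Day -14:

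- Protocol 7.8 says that for every laboratory outcome "mean values from samples obtained on Day -14 and Day 0 will be compared using a two-sided test for comparison".
- The synopsis (Study Design) says serial values will be "compared with each other as well as with values obtained at study entry (Day -14").
- Protocol 3.1 likewise lists study entry among the reference values.

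SAP 8.1 notes that the primary endpoint is measured at all five visits, but in its model "study visit 2 (day 0), 3 (day 30), 4 (day 60), 5 (day 90) is a categorical effect". SAP 8.2 and 8.3 apply the same model to the secondary and laboratory exploratory endpoints. Visit 1 has one inferential use: "For subjects who lack visit 2, the value at visit 1 will be used". SAP 6.3 repeats that rule. By-visit summary statistics are planned. SAP Section 10, which lists changes from the protocol, does not mention the Day -14 comparison.

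**The concern.** With no control arm, the baseline is the only comparator. If the run-in week moved Day 0 away from the usual-care level, that displacement is part of the Day 90 minus Day 0 estimate. A fall would be counted as benefit, and a rise would conceal some.

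The protocol planned a comparison that bears on this, and the Day -14 samples are collected anyway. Under the SAP a reader gets no paired estimate or interval for the Day -14 to Day 0 change, and none for Day 90 against usual care.

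The substitution rule adds a smaller problem. It places usual-care values for some subjects and post-run-in values for others in the same baseline level.

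**Working it through.** **Inputs.** SAP 6.1: "Statistical tests will be conducted at the 0.05 significance level using 2-tailed tests". SAP 3.2: "The proposed study with 30 complete and evaluable subjects would have 80% power to detect a minimum effect size of 0.53", "using 1.5% as the maximum standard deviation expected when measuring DHA levels in plasma", and a detectable rise of 0.8 points. Protocol 11.1: 14 g fat and 10 g MCT per 250 mL. The table is broken in the text, but 14×9 + 46×4 + 17×4 = 378 kcal against 375 stated, which supports the 14 g.

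**1. The plan's own figure.** Paired t-test, n = 30, df = 29, critical t = 2.045, noncentrality 0.53×√30 = 2.90. Power is 80.1%, so the stated 80% reproduces. At 0.8/1.5 = 0.533 it is 80.6%. The 1.5 is therefore treated below as the SD of a within-subject change. That is an assumption, and the figure is for plasma DHA, not erythrocyte DHA+EPA.

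**2. Run-in formula.** MCT share 10/14 = 71%; remaining fat 14 − 10 = 4 g per 250 mL.

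**3. How a shift enters.** For subjects with all three values,

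(Day 90 − Day 0) = (Day 90 − Day -14) − (Day 0 − Day -14).

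A mean run-in change of −d adds d to the primary contrast, and +d subtracts d.

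**4. Illustration only.** The documents give no value for d. Suppose no true change from Day -14 to Day 90, n = 30, and a Day 0 mean lowered by d. The chance of a significant favourable Day 90 − Day 0 result is 1 − F(2.045), where F is the noncentral t distribution with df 29 and noncentrality d√30/SD. The nominal rate is 2.5%.

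| Assumed fall d | d / 0.8 | SD 1.5 | SD 1.0 |
|---|---|---|---|
| 0.1 | 12.5% | 5.4% | 7.6% |
| 0.2 | 25% | 10.5% | 18.4% |
| 0.4 | 50% | 29.2% | 56.3% |

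In simulation (20,000 runs, SD 1.5, falls of 0 to 0.8), the Day 90 − Day -14 contrast kept a rate of 2.3% to 2.6%.

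**5. What the protocol's comparison can show.** The 95% half-width for a paired mean is 2.045×SD/√30 = 0.373 SD, or 0.56 points at SD 1.5. That exceeds every fall in the table. The two-sided test would detect a fall of 0.2 about 11% of the time and a fall of 0.5 about 42% of the time. The contrast also covers a usual-care week. Protocol Table 1 has no Day -7 sample, although the synopsis objective mentions Day -7 values, so the run-in cannot be isolated.

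**6. The change log.** The SAP Section 10 row headed as Protocol 7.8 reproduces the run-in versus treatment ANOVA sentence that closes Protocol 7.7, on GI symptoms. The Day -14 sentence of 7.8 appears nowhere in the log.

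**The case against.** - **The test may be unspecified rather than withdrawn.** SAP 4.2 says that planned analyses identified in the protocol and the SAP will be done, and Section 10 does not list a removal. The table shells named in the SAP contents are not in the text reviewed here. This is fair as far as it goes, but no SAP method or planned table title implements a Day -14 contrast, so the two documents need reconciling either way.
- **Day -14 means will probably be visible.** By-visit summaries are planned. A shift could therefore be suspected, but means alone give no paired estimate or interval.
- **Day 0 is the protocol's own baseline.** It follows a run-in intended to standardise formula and volume (Protocol 4.3). This stands, and it is why the primary contrast should not change.
- **A reader might infer that the run-in lowers the baseline and inflates the result.** The documents do not support that. Usual formulas are only to be recorded, some subjects may already use Peptamen 1.5, and daytime diet and PERT continue. The shift could be nil or upward.
- **A reader might infer that Day -14 is sampled to detect a run-in effect.** Protocol 4.3 gives eligibility screening and characterising the population as its uses, and 4.9.12 to 4.9.14 treat both days as baseline measures. Detecting a run-in effect is not a stated purpose.
- **A reader might infer that adding the contrast would settle the matter.** Step 5 shows that it would not.

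**Conclusion.** The point holds as an unrecorded omission of a protocol comparison, with a conditional consequence. That the SAP specifies no Day -14 contrast and does not log the fact is clear from the text. Whether Day 0 is displaced, by how much and in which direction is unknown.

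Any displacement enters the Day 90 minus Day 0 estimate one for one. The percentages in step 4 rest on assumed falls and on the plan's plasma-DHA figures, so they illustrate sensitivity and do not estimate bias in the erythrocyte primary endpoint. I would expect one week of formula change to matter more for plasma than for erythrocyte endpoints, but the documents give no figure for either, and the same model serves both.

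This warrants a SAP amendment. It does not invalidate the primary analysis.

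**What to change.** 1. Leave the Visit 2 to 5 MMRM and its Day 90 minus Day 0 contrast as they are.
2. For each fatty-acid, vitamin, serum protein and LTE4 endpoint, add supportive paired estimates with 95% CIs for Day 0 minus Day -14 and Day 90 minus Day -14. Use a separate paired analysis or a supportive five-visit model.
3. Report a sensitivity analysis without the Visit 1 substitution.
4. State that a non-significant Day 0 minus Day -14 result does not show absence of a shift (half-width about 0.56 points at n = 30 and SD of change 1.5), and that the contrast also spans a usual-care week.
5. Describe results relative to usual care from the Day -14 contrast, without making it a new success criterion.
6. Record the departure from Protocol 7.8 in SAP Section 10 with a reason, and correct the misattributed row.

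The cost is SAP wording and a few output tables, with no new data. Keeping Visit 1 out of the primary model avoids raising its unstructured covariance from 4×5/2 = 10 to 5×6/2 = 15 parameters with about 30 subjects, which could trigger the fallback structures in SAP 8.1. The fix does not address the separate matter that the treatment formula and the device start together at Day 0.
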